## 16.3. Source Documents

The patient source documentation should include hospital reports, doctor's/nurse's notes, laboratory results, reports of special examinations, the signed consent forms, consultants letters. The Investigator is asked to report the following information in the patient's medical file (source documents) according to Sources Data Agreement signed by the Principal Investigator of each Investigational site:

- Mention of patient's participation in the study, patient code and treatment number, date and process of signature of informed consent form
- Demographic data (partial date of birth, sex, name)
- Past medical and surgery history
- Past and recent treatments
- Concomitant treatments at inclusion

- Change in concomitant treatments throughout the study
- Date of each study visit
- Date of the final visit
- Date and reason of premature withdrawal
- All data related to study procedures
- Any non-serious ADEs and SADEs occurred during the time course of the study and study drug-related SAEs which occurred after the completion of the study
- Any pregnancy occurring during the study or within 14 days of completing the study
- Any data that could be judged by the Investigator as relevant

This list is not exhaustive.

## 16.4. Data Collection

The Principal Investigator must maintain detailed records on all patients who provided informed consent. Data for screened and enrolled patients will be entered into eCRFs, designed according to the protocol. Review of the eCRFs will be completed remotely by Santen (or designee). At designated intervals, a study monitor will perform source data verification on site. During those visits, Santen (or designee) will monitor the patient data recorded in the eCRF against source documents at the study site. Santen (or designee) will review and evaluate eCRF data and use standard system edits, and may use centralised monitoring evaluations, to detect errors in data collection. At the end of the stud, a copy of the completed eCRFs will be sent to the site to be maintained as study records.

## 17. PUBLICATION POLICY

The investigator is obliged to provide the Sponsor with complete test results and all data derived by the investigator from the study. During the study, only the Sponsor may make study information available to other study investigators or to regulatory agencies, except as required by law or regulation. Except as otherwise allowable in the clinical study site agreement, any public disclosure (including publicly accessible websites) related to the protocol or study results, other than study recruitment materials and/or advertisements, is the sole responsibility of the Sponsor.

The Sponsor may publish any data and information from the study (including data and information generated by the investigator) without the consent of the investigator. Any published data will be written in accordance with prevailing guidelines including International Committee of Medical Journal Editors and Good Publication Practice for Communicating Company-Sponsored Medical Research. Manuscript authorship for any peer-reviewed publication will appropriately reflect contributions to the production and review of the document. All publications and presentations must be prepared in accordance with this section and the Master Services Agreement or equivalent agreement. In the event of any discrepancy between the protocol and the Master Services Agreement or equivalent agreement will prevail.

# 19. APPENDICES

# 19.1. Appendix A-I Modified Oxford Scale

Grading of corneal fluorescein staining, corneal fluorescein clearing and staining of the nasal and temporal interpalpebral conjunctiva

The Grade 0 corresponds to none staining dots

Grading of corneal fluorescein staining, corneal fluorescein clearing and staining of the nasal and temporal interpalpebral conjunctiva according to the modified Oxford scale.

OD				OS	
Temporal		Nasal	Nasal		Temporal
interpalpebral	Corneal area	interpalpebral	interpalpebral	Corneal area	interpalpebral
conjunctiva		conjunctiva	conjunctiva		conjunctiva
A	В	C	C	В	A
A	B*	С	С	B*	A
0 0.5 1 2	B* 0 0.5 1 2	C 0 0.5 1 2	C 0 0.5 1 2	B* 0 0.5 1 2	A 0 0.5 1 2
0 0.5 1 2				0 0.5 1 2	0 0.5 1 2
0 0.5 1 2			C 0 0.5 1 2 0 0 0.5 1 5		
0 0.5 1 2		3 4 5	3 4 5	0 0.5 1 2	0 0.5 1 2

Staining scores range from 0-5 for the cornea, temporal and nasal conjunctiva and 0-15 for the total exposed ocular surface.

# 19.2. Appendix A-II Slit lamp examination

External ocular examination and undilated biomicroscopy will be performed using a slit lamp. The patient will be seated while being examined; grading of the Meibomian glands, lids, lashes, conjunctiva, tear film debris, anterior chamber and lens will be done according to the following scales:

Meibomian glands (evaluation of the central ten Meibomian gland openings in the mid-portion of the upper eyelid):

- 0 = None (none are plugged).
- 1 = Mild (1 to 2 glands are plugged).
- 2 = Moderate (3 to 4 glands are plugged).
- 3 = Severe (All glands are plugged).

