## Safety:

- Adverse event (AE) and Serious AE (SAE)
- Best Corrected Distance Visual Acuity (BCDVA)
- Intraocular Pressure (IOP)
- Local ocular tolerance (slit lamp)

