#### Ocular

- 1. CFS score ≥4 on a modified Oxford scale
- 2. Ocular hypertension or glaucoma requiring IOP-lowering medication(s)
- 3. History of ocular trauma, infection or ocular inflammatory condition within the last 3 months before the screening visit.
- 4. Severe blepharitis and/or severe meibomian gland disease
- 5. Filamentary keratitis
- 6. Any ocular surface anomaly not related to DED
- 7. Active ocular infection or history of ocular allergy or ocular herpes
- 8. Patient with only one sighted eye or with a best corrected distance visual acuity  $\leq 1/10$
- 9. Use of any topical ocular treatment other than study device during the study (all non-study topical ocular treatment(s) must be stopped at the screening visit)
- 10. Onset of lid hygiene (whatever the method) less than 2 months before the Screening visit
- 11. Use of topical corticosteroids one month before the Screening Visit

- 12. Use of isotretinoin, ciclosporin, tacrolimus, sirolimus, pimecrolimus or ocular cauterisation procedures 2 months before the screening visit and throughout the study
- 13. Use of VISMED® within 6 weeks prior to the screening visit
- 14. Refractive surgery (e.g. LASIK, LASEK, PRK) within 6 months and/or any other ocular laser/surgery within 3 months prior to the screening visit and during the study
- 15. Insertion of temporary punctal plug(s) within 2 months prior to the Screening visit or permanent occlusion of lacrimal puncta on one or both sides
- 16. Known hypersensitivity to any of the components of the study device or investigational products

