## 11.1.3. Slit lamp examination

External ocular examination and undilated biomicroscopy will be performed using a slit lamp. The patient will be seated while being examined; grading of the Meibomian glands, lids, lashes, conjunctiva, tear film debris, anterior chamber and lens will be done according the scales in Appendix A-II Slit lamp examination.

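### The Meibomian gland item in Appendix A-II evaluates ten openings but gives no grade for 5 to 9 plugged glands

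*Protocol*

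**What the plan says.** Protocol section 11.1.3 lists the structures to be graded at the slit lamp and states that this "will be done according the scales in Appendix A-II Slit lamp examination". In that appendix (section 19.2) the Meibomian item is defined as "evaluation of the central ten Meibomian gland openings in the mid-portion of the upper eyelid", followed by four grades:

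- The scale starts at "0 = None (none are plugged", for an eye with no finding.
- One step up is "1 = Mild (1 to 2 glands are plugged", the second of the four.
- The third step is "2 = Moderate (3 to 4 glands are plugged", where the counted bands end.
- The scale then goes straight to its top step, "3 = Severe (All glands are plugged".

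The synopsis lists "Local ocular tolerance (slit lamp" among the safety criteria. Section 5.3.2.2 makes local tolerance a safety and tolerability endpoint, and section 12.7.2 has the slit lamp data summarised by treatment group, separately for study eye and fellow eye, at the visits where they are measured. Table 3 places the slit lamp examination at V1, V2, V4 and V5, but not at V3 (Day 14). Section 9 requires assessments in both eyes.

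Section 11.2.1.1 names certain changes in biomicroscopy grade as possible signs of an adverse event: from no finding to moderate or severe, and from mild to severe. It also lets the investigator record milder changes.

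**The concern.** The protocol itself fixes this scale. For an eye with 5 to 9 plugged glands, the scale applied exactly returns no value. The examiner must call the eye moderate, call it severe or leave the item blank, and nothing in the protocol says which.

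Two things are at stake. First, the Meibomian part of the local tolerance summary may mix eyes graded by different private conventions at different centres. The protocol asks for a grade, so if the eCRF records only that, no later analysis rule can recover whether a 2 or a 3 stood for 4, 6 or 10 plugged glands. Second, the adverse event prompt in section 11.2.1.1 depends on the grade. For an eye in the gap, whether the prompt is met can turn on the examiner's choice.

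**Working it through.** The protocol gives no figure to reproduce here. The check is an enumeration.

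**Inputs (Appendix A-II).** Ten openings are evaluated, so the plugged count can be any whole number from 0 to 10, which is 11 values. The four grade definitions are those quoted above, and with ten openings the top grade means a count of 10.

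| Plugged count (of 10) | Grade as printed |
|---|---|
| 0 | 0 |
| 1, 2 | 1 |
| 3, 4 | 2 |
| 5, 6, 7, 8, 9 | none |
| 10 | 3 |

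Counts with a grade: 1 + 2 + 2 + 1 = 6 of 11. Counts without a grade: 11 − 6 = 5 of 11, or 5/11 = 45%. This is a share of possible counts, not of eyes.

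**Is the gap closed elsewhere?** No. Section 11.1.3 only refers back to the appendix, and no other section adds a rule. The four grade lines are complete and in sequence, with no sign of lost or blacked-out text.

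**Which part is at fault?** The text cannot settle this. If five openings were evaluated, the same bands would cover every count: 0; 1 to 2; 3 to 4; and all, meaning 5. The inconsistency may therefore lie in the number of openings or in the bands.

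**Reach.** Appendix A-II contains nine scales: Meibomian glands, lid erythema, lid oedema, lashes, conjunctival erythema, conjunctival oedema, tear film debris, anterior chamber and lens. This point concerns one of them. For the 80 planned patients, the item would be graded up to 80 × 2 eyes × 4 visits = 640 times. How many of these gradings would fall at 5 to 9 cannot be derived from the protocol.

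**Effect on the adverse event prompt.** Take an eye that ends with 5 to 9 plugged glands.

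- Starting at 0: calling the result moderate or severe meets the prompt either way. If the item is left blank, the prompt cannot be applied.
- Starting at 1 or 2 (mild): the prompt is met if the result is called severe and not met if it is called moderate. The same finding gives opposite answers.

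**The case against.** The best case on the other side is that the defect is small. It affects one of nine scales in a descriptive safety examination. The labels are ordinal, so most examiners would probably choose grade 2 or 3, and blanks are speculation. Investigators are masked (section 7.8), so any misclassification is unlikely to favour one arm. Section 11.2.1.1 leaves room for judgement, so a clinically relevant worsening can be recorded whatever grade is written down. All of this stands, and it limits the consequence. It does not supply the missing rule: choosing between 2 and 3 is exactly what centres may do differently, and judgement softens the prompt without standardising it.

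A reader might draw three stronger conclusions that the protocol does not support:

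- **That 45% of eyes would be ungradable.** The figure counts possible values. The share of eyes is unknown, and exclusion criterion 4 probably thins the upper end at entry, by an amount the protocol does not state.
- **That the local tolerance endpoint fails.** The other eight scales are untouched by this point.
- **That eligibility is affected.** Exclusion criterion 4 in section 7.2 bars "Severe blepharitis and/or severe meibomian gland disease" and shares the word severe with grade 3. It does not cite Appendix A-II, and the appendix has no blepharitis scale for the other half of the same criterion, which suggests clinical judgement. A link to this scale would be an assumption and is not claimed here.

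**Conclusion.** The point holds for the Meibomian item. As printed, the number of openings and the grade bands do not fit together, and 5 of 11 possible counts have no grade. This is an error in a rule the protocol fixes, not detail that could wait for a statistical analysis plan.

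Its consequence is limited to inconsistent grading of one descriptive safety item at V1, V2, V4 and V5, and to an undefined adverse event prompt for eyes in the gap. The primary ocular surface staining analysis, the sample size and the non-inferiority conclusion do not use this item and are unaffected.

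The enumeration rests on the printed text alone. The practical size depends on how many study eyes have 5 to 9 plugged glands, which the protocol does not give. That centres would diverge is a reasonable expectation, not something the protocol shows.

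**What to change.** Before the first patient is examined, the sponsor should reconcile the number of openings evaluated with the grade bands in Appendix A-II, and make the same correction in the eCRF, so that every possible count falls in exactly one grade. Whether the number of openings or the bands should change is for the sponsor's ophthalmology lead to decide; the protocol does not show which is wrong.

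The cost is about one line in the appendix and the matching eCRF item. It adds no procedure, visit or patient and leaves the analysis unchanged.

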## Lid - Erythema

- 0 = None (normal).
- 1 = Mild (redness localised to a small region of the lid(s) margin OR skin).
- 2 = Moderate (redness of most or all lid margin OR skin).
- 3 = Severe (redness of most or all lid margin AND skin).
- 4 = Very severe (marked diffuse redness of both lid margin AND skin).

#### Lid - Oedema

- 0 = None (normal).
- 1 = Mild (localised to a small region of the lid).
- 2 = Moderate (diffuse, most or all lid but not prominent/protruding).
- 3 = Severe (diffuse, most or all lid AND prominent/protruding).
- 4 = Very severe (diffuse AND prominent/protruding AND reversion of the lid).

#### Lashes

- 0 = Normal
- 1 = Abnormal (specify)

## Conjunctiva – Erythema

- 0 = None (normal).
- 1 = Mild (a flush reddish colour predominantly confined to the palpebral or bulbar conjunctiva).
- 2 = Moderate (more prominent red colour of the palpebral or bulbar conjunctiva).
- 3 = Severe (definite redness of palpebral or bulbar conjunctiva).

ALOCROSS® Protocol Version 2
ALHENA study 06 July 2020

## Conjunctiva - Oedema

- 0 = None (normal).
- 1 = Mild (slight localised swelling).
- 2 = Moderate (moderate/medium localised swelling or mild diffuse swelling).
- 3 = Severe (severe diffuse swelling).
- 4 = Very severe (very prominent/protruding diffuse swelling).

#### Tear Film Debris

- 0 = None (absence of debris).
- 1 = Mild (presence of debris in inferior tear meniscus).
- 2 = Moderate (presence of debris in inferior tear meniscus and in tear film overlying cornea).
- 3 = Severe (presence of debris in inferior tear meniscus and in tear film overlying cornea. Presence of mucus strands in inferior fornix of on bulbar conjunctiva).
- 4 = Very severe (presence of debris in inferior tear meniscus and in tear film overlying cornea. Presence of numerous AND/OR adherent mucus strands in inferior fornix and on bulbar conjunctiva or filamentary keratitis).

## **Anterior Chamber Inflammation**

- 0 = None (no Tyndall effect).
- 1 = Mild (Tyndall effect barely discernible).
- 2 = Moderate (Tyndall beam in the anterior chamber is moderately intense).
- 3 = Severe (Tyndall beam in the anterior chamber is severely intense).

#### Lens

- 0 = No opacification (normal lens).
- 1 = Mild lens opacification.
- 2 = Moderate lens opacification.
- 3 = Severe lens opacification.

# 19.3. Appendix A-III Visual Analog Scale (VAS)\_Symptoms of Ocular Discomfort

The patient will be asked to assess each symptom regarding ocular discomfort unrelated to instillation among a list of 7 symptoms, i.e. itching, foreign body sensation or sandy feeling or grittiness, photophobia, burning/stinging, eye dryness, pain or ocular discomfort and sticky feeling. The patient will be asked to rate each ocular symptoms by placing a vertical mark on the horizontal line to indicate the level of each ocular symptoms.

0% corresponds to 'no discomfort" and 100% corresponds to "maximal discomfort".

The response will be measured in % between 0 - 100%, on a 100 mm line.

Itching	0% _	50%	100%
Foreign body sensation or sandy feeling or grittiness	0%	50%	100%
Photophobia	0% 	50%	100%
Burning/stinging	0% 	50%	100%
Eye dryness	0%	50%	100%
Pain or ocular discomfort	0%	50%	100%
Sticky feeling	0% _	50%	100%

ALOCROSS® ALHENA study

# 19.4. Appendix A-IV National Eye Institute Visual Function Questionnaire (NEI VFQ-25)

The NEI-VFQ-25 is self-administered and should be completed by the patient.

PB/SA

National Eye Institute Visual Functioning Questionnaire - 25 (VFQ-25)

version 2000

(SELF-ADMINISTERED FORMAT)

January 2000

RAND hereby grants permission to use the "National Eye Institute Visual Functioning Questionnaire 25 (VFQ-25) July 1996, in accordance with the following conditions which shall be assumed by all to have been agreed to as a consequence of accepting and using this document:

- Changes to the NEI VFQ-25 July 1996 may be made without the written permission of RAND. However, all such changes shall be clearly identified as having been made by the recipient.
- 2. The user of this NEI VFQ-25 July 1996 accepts full responsibility, and agrees to hold RAND harmless, for the accuracy of any translations of the NEI VFQ-25 Test Version July 1996 into another language and for any errors, omissions, misinterpretations, or consequences thereof.
- The user of this NEI VFQ-25 July 1996 accepts full responsibility, and agrees to hold RAND harmless, for any consequences resulting from the use of the NEI VFQ-25.
- 4. The user of the NEI VFQ-25 July 1996 will provide a credit line when printing and distributing this document or in publications of results or analyses based on this instrument acknowledging that it was developed at RAND under the sponsorship of the National Eye Institute.
- No further written permission is needed for use of this NEI VFQ-25 July 1996.

7/29/96

© R 1996

English (UK)\_Mapi Research Institute\_D2285\_item16a:2980

version 2000

The following is a survey with statements about problems which involve your eyesight or feelings that you have about your eye condition. After each question please choose the response that best describes your situation.

Please answer all the questions as if you were wearing your glasses or contact lenses (if any).

Please take as much time as you need to answer each question. All your answers are confidential. As the purpose of this survey is to improve our knowledge about eyesight problems and how they affect your quality of life, your answers must be as accurate as possible. Remember, if you wear glasses or contact lenses, please answer all of the following questions as if you were wearing them.

#### INSTRUCTIONS:

- In general we would like to have people try to complete these forms on their own. If you find that you need assistance, please feel free to ask the project staff and they will assist you.
- Please answer every question (unless you are asked to skip questions because they do not apply to you).
- Answer the questions by circling the appropriate number.
- If you are unsure of how to answer a question, please give the best answer you can and make a comment in the left margin.
- Please complete the questionnaire before leaving the centre and give it to a member of the project staff. Do not take it home.
- If you have any questions, please feel free to ask a member of the project staff, and they will be glad to help you.

#### STATEMENT OF CONFIDENTIALITY:

All information that would permit identification of any person who completed this questionnaire will be regarded as strictly confidential. Such information will be used only for the purposes of this study and will not be disclosed or released for any other purposes without prior consent, except as required by law.

© R 1996

English (UK)\_Mapi Research Institute\_ID2285\_item16a:2980

- 2 -

version 2000

# Visual Functioning Questionnaire - 25

#### PART 1 - GENERAL HEALTH AND VISION

1. In general, would you say your health is:

	(Circle On	e)
Excellent		1
Very Good		2
Good		3
Fair		4
Poor		5

2. At the present time, would you say your eyesight in both eyes (with glasses or contact lenses, if you wear them) is excellent, good, fair, poor, or very poor, or are you completely blind?

	(Circle On	e)
Excellent		1
Good		2
Fair		3
Poor		4
Very Poor		5
Completely Blin	d	6

© R 1996

English (UK)\_Mapi Research Institute\_ID2285\_item16a:2980

2	•	version	2000
J	) -	version	ZUUU

3.	How often are	you concerned	about	your e	vesight?

(Circle C	ne)
None of the time	1
A little of the time	2
Some of the time	3
Most of the time	4
All of the time?	5

4. How much pain or discomfort have you had in and around your eyes (for example, burning, itching, or aching)?

(Circle C	)ne)
None	1
Mild	2
Moderate	3
Severe	4
Very severe?	5

#### PART 2 - DIFFICULTY WITH ACTIVITIES

The next questions are about how much difficulty, if any, you have doing certain activities wearing your glasses or contact lenses if you use them for those activities.

5. How much difficulty do you have reading ordinary print in newspapers?

(Circ	ile One)
No difficulty at all	1
A little difficulty	2
Moderate difficulty	3
Extreme difficulty	4
Stopped doing this because of your eyesight	5
Stopped doing this for other reasons or not interested in doing this	6

© R 1996

60

English (UK)\_Mapi Research Institute\_D2285\_item16a:298

6.	How much difficulty do you have doing work or hobbies that require
	you to see well close up, such as cooking, sewing, fixing things
	around the house, or using hand tools?

(Circ	de One)
No difficulty at all	
A little difficulty	2
Moderate difficulty	3
Extreme difficulty	4
Stopped doing this because of your eyesight	5
Stopped doing this for other reasons or not interested in doing this	6

 Because of your eyesight, how much difficulty do you have finding something on a crowded shelf?

(Circ	le One)
No difficulty at all	1
A little difficulty	2
Moderate difficulty	3
Extreme difficulty	4
Stopped doing this because of your eyesight	5
Stopped doing this for other reasons or not interested in doing this	6

8. How much difficulty do you have reading street signs or the names of shops?

(Cir	cle One)
No difficulty at all	1
A little difficulty	2
Moderate difficulty	3
Extreme difficulty	4
Stopped doing this because of your eyesight	5
Stopped doing this for other reasons or not interested in doing this	6

© R 1996

9.	Because of your eyesight, how much difficulty do you have going
	down steps, stairs, or curbs in dim light or at night?

(Circ	le One)
No difficulty at all	1
A little difficulty	2
Moderate difficulty	3
Extreme difficulty	4
Stopped doing this because of your eye sight $\ldots$	5
Stopped doing this for other reasons or not interested in doing this	6

10. Because of your eyesight, how much difficulty do you have noticing objects on the side while you are walking straight ahead?

(Circ	le One)
No difficulty at all	1
A little difficulty	2
Moderate difficulty	3
Extreme difficulty	4
Stopped doing this because of your eyesight	5
Stopped doing this for other reasons or not interested in doing this	6

11. Because of your eyesight, how much difficulty do you have seeing how people react to things you say?

(Circ	le One)
No difficulty at all	1
A little difficulty	2
Moderate difficulty	3
Extreme difficulty	4
Stopped doing this because of your eyesight	5
Stopped doing this for other reasons or not interested in doing this	6

© R 1996

English (UK)\_Mapi Research Institute\_ID2285\_item16a:2980

- 6 - version 2000

12.	Because of your eyesight, how much difficulty do you have picking
	out and matching your own clothes?

(Circ	le One)
No difficulty at all	1
A little difficulty	2
Moderate difficulty	3
Extreme difficulty	4
Stopped doing this because of your eyesight	5
Stopped doing this for other reasons or not interested in doing this	6

13. Because of your eyesight, how much difficulty do you have visiting with people in their homes, at parties, or in restaurants?

(Circ	cle One)
No difficulty at all	1
A little difficulty	2
Moderate difficulty	3
Extreme difficulty	4
Stopped doing this because of your eyesight	5
Stopped doing this for other reasons or not interested in doing this	6

14. Because of your eyesight, how much difficulty do you have going out to see films, plays or sports events?

(Circ	le One)
No difficulty at all	1
A little difficulty	2
Moderate difficulty	3
Extreme difficulty	4
Stopped doing this because of your eyesight	5
Stopped doing this for other reasons or not interested in doing this	6

© R 1996

		- 7 - ve	rsion 2000
15.	Are y	you currently driving , at least once in a while?	
		(Circle One)	
		Yes 1 Skip To 0	Q 15c
		No 2	
	15a.	IF NO: Have you never driven or have you given up dri	ving?
		(Circle One)	
		Never drove 1 Skip To I	Part 3, Q 17
		Gave up 2	
	15b.	IF YOU HAVE GIVEN UP DRIVING: Was that mainly bed your eyesight, for some other reason, or because of your eyesight and other reasons?	
		(Circle One)	
		Mainly eyesight 1 Skip To k	Part 3, Q 17
		Mainly other reasons 2 Skip To I	Part 3, Q 17
		Eyesight and other reasons 3 Skip To I	Part 3, Q 17
	15c.	IF CURRENTLY DRIVING: How much difficulty do you driving during the daytime in familiar places? Would y you have:	
		(Circle One)	
		No difficulty at all 1	
		A little difficulty 2  Moderate difficulty 3	
		Extreme difficulty 4	
		•	

© R 1996

	- 8 -	version 200
16. How much difficulty do	you have driving at night ?	
		(Circle One)
	No difficulty at all	1
	A little difficulty	2
	Moderate difficulty	3
	Extreme difficulty	4
	Have you stopped doing this of your eyesight	
	Have you stopped doing this reasons or not interested doing this	lin
	you have driving in difficult cor ng the rush hour, on the motorw	
		(Circle One)
	No difficulty at all	
	A little difficulty	2
	Moderate difficulty	3
	Extreme difficulty	4
	Have you stopped doing this of your eyesight?	
	Have you stopped doing this reasons or are you not in doing this?	terested in

© R 1996

-9-

version 2000

